Platelets	$<100 \times 10^9/L$ or 100,000/mm ³
Non-hematological toxicity	Any > Grade 2 except for inadequately treated nausea and/or vomiting
b): Do not administer any Day 8 treatment where:	
Absolute Neutrophil Count	$<0.75 \times 10^9/L$ or 750/mm ³
Platelets	$<75 \times 10^9/L$ or 75,000/mm ³
Non-hematological toxicity	Any > Grade 2 except for inadequately treated nausea and/or vomiting
c): Do not administer any subsequent Day 1 treatment where:	
Absolute Neutrophil Count	$<1.0 \times 10^9/L$ or 1,000/mm ³
Platelets	$<75 \times 10^9/L$ or 75,000/mm ³
Non-hematological toxicity	Any > Grade 2 except for inadequately treated nausea and/or vomiting

If the dose cannot be administered as planned due to treatment-related toxicity, the dose should be delayed according to the following instructions.

Day 1 of each cycle: If treatment cannot be administered on Day 1, the dosing should be delayed until recovery to above the values in [Table 1](#) or Grade ≤ 2 as appropriate (for Cycle 1 & subsequent cycles). The Day 1 dose will be rescheduled for when the criteria for treatment administration are met. The dose level may have to be reduced following a dose delay in accordance to the instructions for dose reduction ([Table 2](#) and [Table 3](#)).

Day 8 of each cycle: If treatment cannot be administered on Day 8, the dosing should be delayed until recovery to above these values ([Table 1](#)). The Day 8 dosing will be **delayed for a maximum of 7 days** and as follows:

- If recovery occurs on or before Day 15, dosing will be resumed at the next lower dose level ([Table 3](#)) and this will be the new Day 8.
- If hematological or non-hematological toxicity has not resolved to the above values on Day 15, the second administration in the cycle will be omitted. Dosing will be resumed at the next lower dose level ([Table 3](#)) and as scheduled on Day 1 of the next cycle if recovery has occurred to the above values.

Please note, use of hematopoietic growth factors is not permitted in Cycle 1 and is only permitted in subsequent cycles as per institutional guidelines.

The treatment will be permanently reduced to the next lowest dose level ([Table 3](#)) after the occurrence of any of the following events:

Table 2 Criteria for Reduction of Eribulin Mesylate to the Next Lowest Dose Level

Absolute Neutrophil Count	Grade 4 neutropenia >7 days Grade 3 or 4 febrile neutropenia and/or infection requiring treatment with antibiotics and/or growth factors
----------------------------------	---

Platelets	Grade 4 thrombocytopenia Grade 3 thrombocytopenia requiring platelet or blood transfusion or both
Non-hematological toxicity	Grade 3 or 4 non-hematological toxicities (attributable to study drug); except Grade 3 hypophosphatemia, hypokalemia, hypocalcemia or hypomagnesemia that respond to supplementation

Table 3 Eribulin Mesylate Dose Modifications

Dose modifications based on adverse events (AEs) for eribulin mesylate (Starting dose determined by COG protocol ADVL1314/Eisai Study E7389-A001-113; 1.4 mg/m²).

Dose Level	Eribulin mesylate (mg/m²)
0*	1.4
-1	1.1
-2	0.8

* Dose level 0 refers to the starting dose.

If hematological toxicities do not recover following a dose reduction to dose level -1 and the use of hematopoietic growth factors the dose should be reduced to dose level -2. If non-hematological toxicities do not recover following a dose reduction to dose level -1, a second dose reduction to dose level -2 should be made. If either hematologic or non-hematologic toxicities do not recover despite two dose reductions, the subject should be discontinued from treatment. However, if the subject is deemed to have clinical benefit, continuation of treatment may be discussed with the sponsor.

Do not re-escalate dose after the dose level has been reduced.

Duration of Treatment

Subjects may remain on study treatment as long as they do not meet any of the following criteria: 1) experience objective progression of disease (according to RECIST 1.1); 2) exhibit no clinical benefit (in the opinion of the investigator); 3) experience unacceptable toxicity leading to withdrawal from the study; 4) withdraw or are withdrawn from the study for any reason, or; 5) termination of the study program, whichever occurs first.

As long as the subject is still receiving clinical benefit and has not experienced intolerable toxicity, he or she can continue to receive study treatment. An end of treatment (EOT) visit within 28 days after last date of receiving investigational drug will be performed for subjects who discontinue study treatment. After discontinuation of treatment and completion of the EOT visit, subjects will be followed up for survival approximately every 12 weeks for 1 year, and then annually thereafter, unless consent is withdrawn or death.

Concomitant Drug/Therapy

Supportive care will be allowed as per institutional guidelines. Growth factors that support platelet or white blood cell number or function can only be administered in accordance with dose modification guidelines or for culture proven bacteremia or invasive fungal infection. Prophylactic granulocyte colony-stimulating factor should NOT be administered during Cycle 1.

Subjects should not receive any other anticancer therapy (including chemotherapy, radiation therapy, immunotherapy or biologic therapy) or investigational agents while receiving study drug. If these therapies are administered, the subject will be removed from the study.

Assessments

Efficacy Assessments

Tumor response and progression will be evaluated according to RECIST 1.1 criteria. Copies of all scans for tumor assessments will be sent to an imaging core laboratory designated by the sponsor for quality assessment, archiving and potential independent review. Tumor assessment scans will be performed following the guidelines provided by the imaging core laboratory. Decisions concerning treatment discontinuation due to progressive disease will be based on investigator assessment.

Tumor assessments (CT chest, and CT or MRI abdomen, pelvis, and other known or suspected sites or disease) will be performed during screening and then every 6 weeks (within the sixth week) on a fixed schedule from the date of first study drug administration. Magnetic resonance imaging scans may be used instead of CT scans for abdomen and pelvis; however, chest must be assessed using CT. Scans that were performed within the screening window, but before informed consent, may be used if they were acquired consistent with the guidelines provided by the imaging core laboratory. The same method of assessment must be used at all time-points as used at pre-study. Partial and complete responses will be confirmed at least 4 weeks after initial documentation of PR or CR typically on the next consecutive scheduled tumor assessment. After 24 weeks subjects with CR, PR or stable disease (SD) may have imaging decreased to every 9 weeks (within the ninth week).

A bone scan or ¹⁸FDG-PET/CT scan will be performed during screening to establish a baseline (a historical bone scan performed within 6 weeks before study drug administration is acceptable), approximately every 24 weeks (in conjunction with a scheduled tumor assessment visit) and as clinically indicated. Lesions identified on bone scans should be followed with cross-sectional imaging.

Brain scans will be performed as clinically indicated to assess potential CNS disease and/or metastases. For subjects with a history of protocol-eligible treated brain metastases, a brain scan will be required at screening and all tumor assessment time points (eg, every 6 weeks).

Subjects who discontinue treatment without objective evidence of disease progression will continue to have tumor assessments, per the schedule of assessments, until disease progression, death, or initiation of another anticancer therapy.

Pharmacokinetic Assessments

Blood samples will be collected for PK analysis of eribulin as follows:

1. Immediately post-infusion on Day 1 of each cycle for the first 3 cycles
2. Pre-infusion and immediately post-infusion on Day 8 of each cycle for the first 3 cycles

Pharmacodynamic, Pharmacogenomic, and Other Biomarker Assessments

Exposure-response Analyses

Following FDA guidance, PK sampling will be conducted in subjects across the pediatric program at regular intervals in order to adequately characterize the PK of eribulin in the pediatric population in the various age cohorts to explore exposure-response relationships for activity/efficacy and safety. The relationship between exposure to eribulin mesylate and AE and efficacy will be explored graphically.

Safety Assessments

Safety assessments will consist of monitoring and recording all adverse events (AEs) according to Common Terminology Criteria for Adverse Events (CTCAE v4.03). This includes listing of all grades (for both increasing and decreasing severity) and serious adverse events (SAEs); regular laboratory evaluation for hematology, blood chemistry, and urine values; periodic measurement of

vital signs, the performance status, and physical examinations.

Other Assessments

ECG monitoring to evaluate RR, PR, QRS, and QT intervals and QTc interval (corrected for heart rate [QTc] using Fridericia's [QTcF] and Bazett's [QTcB] correction factors) at pre-study, during Cycle 1 (pre- and post-infusion Day 1 and Day 8) and as clinically indicated during subsequent cycles and during follow-up (28 days after the last dose of drug).

A full neurological examination will be conducted at Screening. On subsequent cycles an assessment of neuropathy (neuropathy present/absent and CTC AE Grade) will be assessed as part of the physical examination

Bioanalytical Methods

Plasma concentrations of eribulin mesylate will be determined using a validated liquid chromatography coupled with tandem mass spectrometry (LC-MS/MS) method. The lower limit of quantification (LLOQ) is 0.2 ng/mL.

Statistical Methods

Study Endpoints

Primary Endpoints

- Objective response: number of subjects achieving a best objective response of partial or complete response (PR or CR), by up to 24 weeks after all subjects have completed response assessment. Response assessment will be as determined by investigator.

Secondary Endpoints

- PFS: defined as the time from the first dose date to the date of disease progression or date of death (whichever occurs first).
- Safety and tolerability: AEs, SAEs, clinical laboratory values, ECG parameters, vital sign measurements, and performance status.
- DOR: defined as the time from the first date of documented PR or CR to the date of disease progression or date of death (whichever occurs first).
- OS: defined as the time from the first dose date to the date of death.

Exploratory Endpoints

- Exposure of eribulin mesylate.

Analysis Sets

Full Analysis Set (FAS) will consist of all subjects who receive at least 1 dose of study drug.

Safety Analysis Set (SAS) will consist of all subjects who receive at least 1 dose of study drug.

Pharmacokinetic Analysis Set (PAS) will include subjects who have at least 1 evaluable plasma concentration and sufficient dosing information.

Efficacy Analyses

The primary analysis will be based on investigator assessments of tumor response.

The primary analysis is to examine the number of responders within each histology subject cohort. Confirmed response (PR or CR) will be used in this analysis. In each of the histology groups of RMS, NRSTS, and EWS, approximately 15 subjects will be enrolled and treated with eribulin mesylate. Data will be monitored on an ongoing basis; depending on evaluation by the investigators and sponsor, if sufficient responses (partial response [PR] or complete response [CR]) are observed,

then this histology type will be recommended for inclusion in the subsequent study. At the latest, the primary analysis will be performed when approximately 15 subjects have completed 24 weeks of response assessments.

Secondary Efficacy Analyses

The secondary analyses will be to estimate the PFS, DOR, and OS in all cohorts combined. Median PFS, DOR, and OS will be estimated using Kaplan-Meier method.

Pharmacokinetic Analyses

Observed eribulin concentrations from this study will be overlaid with existing observed concentrations and model-predicted 90% prediction intervals at the same dose level from other studies to demonstrate comparability in exposure.

Safety Analyses

Safety analyses will be performed on all subjects who receive at least 1 dose of study drug. It will include safety data collected from screening to data cut-off. Safety data include the incidence and severity of AEs, clinical laboratory test results, performance status, ECG readings, and vital signs measurements.

Vital signs, resting 12-lead ECGs, hematology, clinical chemistry, and urinalysis data will be listed. Descriptive summary statistics (mean, standard deviation, median, minimum, and maximum) of clinical laboratory test results, vital signs measurements, ECG parameters, and changes from Baseline will be presented by cohort and overall. Treatment-emergent abnormal laboratory test results, vital signs, and ECGs will be listed.

All AEs and SAEs will be listed. Treatment-emergent AEs (TEAEs), treatment-related TEAEs, and SAEs will be summarized by cohort, system organ class, preferred term, and CTCAE v. 4.03 grade. QT intervals will be measured from Lead II and will be corrected for heart rate (QTc) using QTcF and QTcB correction factors. The primary QTc parameter will be QTcF. Secondary parameters will be QTcB, QT, QRS, and heart rate.

Interim Analyses

Data will be monitored on an ongoing basis; depending on evaluation by the investigators and sponsor, if sufficient responses (PR or CR) are observed, then this histology type will be recommended for inclusion in the subsequent study.

Sample Size Rationale

A total of 45 subjects will be enrolled. In each of the histology groups of RMS, NRSTS, and EWS, approximately 15 subjects will be enrolled and treated with eribulin mesylate. The sample size is considered sufficient based on clinical judgment and is not obtained from statistical calculation.

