9. Has CNS Disease: Subjects with brain or subdural metastases are not eligible unless the metastases are asymptomatic and do not require treatment or have been adequately treated by local therapy (eg, surgery or radiotherapy) and have discontinued the use of corticosteroids for this indication for at least 4 weeks prior to study drug administration. Confirmation of radiographic stability must be done by comparing the brain scan (CT or MRI) performed during the Screening Period, using the same imaging modality, to a brain scan performed earlier (and following local therapy where applicable). Subjects must be clinically stable. It is not the intention of this protocol to treat subjects with active brain metastases.
Note: CNS imaging is required to confirm eligibility for subjects with a known history of CNS disease.
10. Have had or are planning to have the following invasive procedures:
 - Major surgical procedure or significant traumatic injury within 28 days prior to study drug administration.
 - Laparoscopic procedure or open biopsy within 7 days prior to study drug administration.
 - Central line placement or subcutaneous port placement is not considered major surgery but must be placed at least 2 days prior to study drug administration.
 - Core biopsy, including bone marrow biopsy within 2 days prior to study drug administration.
 - Fine needle aspirate within 3 days prior to study drug administration.
11. Has any serious concomitant illness that in the opinion of the investigator(s) could affect the subject’s safety or interfere with the study assessments.
12. Subjects with known human immunodeficiency virus (HIV); due to lack of available safety data for eribulin therapy in HIV infected subjects.

Study Treatment(s)

Administration of eribulin mesylate by 2-5 min IV infusion at 1.4 mg/m² on Days 1 and 8 of each 21-day cycle. Eribulin may be diluted in up to 100 mL 0.9% sodium chloride, and administered as an IV infusion over 15 minutes (maximum infusion duration), where clinically appropriate.

Criteria for Dosing Modifications

Dose reduction and interruption for eribulin mesylate related toxicity will be performed according to the following instructions.

Treatment will not be administered when any of the following values are recorded ([Table 1](#)).

Table 1 Criteria for Administration of Eribulin Mesylate

a): Do not administer Cycle 1 Day 1 treatment where:

Absolute Neutrophil Count	$<1.0 \times 10^9/L$ or 1,000/mm ³

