9.5.1.5 Pharmacokinetic, Pharmacodynamic, Pharmacogenomic, and Other Biomarker Assessments

9.5.1.5.1 PHARMACOKINETIC ASSESSMENTS

Samples for PK analysis of eribulin will be collected immediately post-infusion on Day 1 each cycle for 3 cycles, and pre-infusion and immediately post-infusion on Day 8 each cycle for 3 cycles (Table 9). Plasma concentrations of eribulin will be tabulated and summarized by dose level and time.

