5.5 Pharmacokinetic, Pharmacodynamic, Pharmacogenomic, and Other Biomarker Analyses

5.5.1 Pharmacokinetic Analyses

Blood samples will be collected for the PK analysis of eribulin as follows:

1. Immediately post-infusion on Day 1 of each cycle for the first 3 cycles;
2. Pre-infusion and immediately post-infusion on Day 8 of each cycle for the first 3 cycles.

Plasma concentrations of eribulin will be tabulated and summarized by histology and time.

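### The PK summary and comparability overlay pool end-of-infusion eribulin concentrations across infusions of 2-5 and up to 15 minutes, and the SAP table also pools dose levels (minor)

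*Protocol*

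**What the plan says.** **Administration.** The Study Treatment(s) part of the protocol synopsis specifies "Administration of eribulin mesylate by 2-5 min IV infusion at 1.4 mg/m² on Days 1 and 8 of each 21-day cycle", and then allows a diluted alternative: "Eribulin may be diluted in up to 100 mL 0.9% sodium chloride, and administered as an IV infusion over 15 minutes (maximum infusion duration". Protocol sections 9.4.1 and 9.4.5 repeat both options. The longer infusion is left to clinical judgment.

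**Sampling.** For each of the first three cycles there is a Day 1 sample ("Immediately post-infusion on Day 1 of each cycle for the first 3 cycles") and a pair of Day 8 samples ("Pre-infusion and immediately post-infusion on Day 8 of each cycle for the first 3 cycles"). Table 9, footnote i, puts the post-infusion ECG before the post-infusion PK sample in Cycle 1 and gives no window for the PK draw.

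**Summary.** Protocol 9.5.1.5.1 states: "Plasma concentrations of eribulin will be tabulated and summarized by dose level and time". SAP 5.5.1 states: "Plasma concentrations of eribulin will be tabulated and summarized by histology and time".

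**Overlay.** The synopsis paragraph on PK analyses says that this study's concentrations will be "overlaid with existing observed concentrations and model-predicted 90% prediction intervals at the same dose level from other studies", in order to show comparable exposure. Neither protocol 9.7.1.7.1 nor the SAP repeats this.

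No section stratifies or flags concentrations by infusion duration, or says which infusion and sampling times the prediction intervals assume.

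**The concern.** Eribulin distributes while it is being infused. At a given dose, a sample drawn at the end of a 15-minute infusion is therefore expected to be lower than one drawn at the end of a 2-5-minute infusion, with no difference in clearance or total exposure. Two-thirds of the scheduled samples are of this kind.

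If the two durations share a summary row, the row mean depends on how many longer infusions it contains. Their use is decided case by case at about 40 sites and need not balance across histologies, so an apparent PK difference between cohorts could come from administration practice alone. The overlay has the same weakness: a departure from the reference data, or agreement with it, could partly reflect a different mix of durations. The SAP table adds a second source of mixing, because children at reduced dose levels fall in the same row as children at the starting dose.

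At stake is the interpretation of the exploratory exposure results and of the comparability display.

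**Working it through.** The plan states no figure for this point, so there is none to reproduce.

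**Step 1. Sample count (protocol synopsis; Table 9, footnote h).** Day 1 gives 1 × 3 = 3 post-infusion samples. Day 8 gives 1 × 3 = 3 pre-infusion and 1 × 3 = 3 post-infusion samples. The total is 9, of which 6 (67%) are post-infusion. With 45 children the maximum is 45 × 6 = 270 of 45 × 9 = 405.

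**Step 2. Direction.** For a constant-rate infusion of length T and a mono-exponential initial phase, the end-of-infusion concentration per unit dose is proportional to

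f(T) = (1 − exp(−kT)) / (kT), with k = ln 2 / half-life.

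f falls as T rises for every k > 0, so the direction does not depend on the half-life.

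**Step 3. Size.** The documents give no initial half-life, so a range is assumed. For a 10-minute half-life, k = 0.0693 per minute, f(15) = 0.622, f(3.5) = 0.888, and the ratio is 0.700. In full:

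| Assumed half-life (min) | 15 vs 2 min | 15 vs 3.5 min | 15 vs 5 min |
|---|---|---|---|
| 5 | 0.482 | 0.531 | 0.583 |
| 10 | 0.666 | 0.700 | 0.736 |
| 20 | 0.807 | 0.828 | 0.849 |
| 30 | 0.865 | 0.880 | 0.895 |
| 60 | 0.929 | 0.937 | 0.945 |

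A bi-exponential variant (assumed fast share 0.8-0.95, fast half-life 5-30 minutes, slow half-life 40 hours) gives 15-minute to 2-minute ratios of 0.51-0.89 with immediate sampling and 0.58-0.90 with a 10-minute delay.

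**Step 4. Effect on a pooled mean.** If a share p of infusions takes 15 minutes and the rest 3.5 minutes, the mean shifts by p × (ratio − 1). The documents give no p.

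| Assumed p | Half-life 10 min (0.700) | Half-life 30 min (0.880) |
|---|---|---|
| 5% | −1.5% | −0.6% |
| 10% | −3.0% | −1.2% |
| 20% | −6.0% | −2.4% |
| 50% | −15.0% | −6.0% |

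**Step 5. Two other sources in the same rows.** The protocol's dose levels are 1.4, 1.1 and 0.8 mg/m². Under dose-proportional concentrations the reduced levels give ratios of 1.1/1.4 = 0.79 and 0.8/1.4 = 0.57, and the SAP table does not separate them. For a late draw, a 5-minute delay at a 10-minute half-life multiplies the concentration by 2^(−5/10) = 0.71, about the same as the duration effect at that half-life.

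**Step 6. Samples not affected.** The Day 8 pre-infusion samples come about a week after the previous dose, so a difference of 10 to 13 minutes in that infusion's length is negligible for them.

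**The case against.** The case against making much of this is substantial, and most of it stands.

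- A reader might infer that a child infused over 15 minutes will look under-exposed against reference data from 2-5-minute infusions. The documents do not support that: the infusion durations in the reference studies are not stated. If those studies had a similar mix, much of the bias in the overlay would cancel.
- A reader might also infer that the exploratory exposure endpoint rests mainly on these peaks. It is defined only as exposure to eribulin, and protocol 9.4.6.1.1 expresses exposure as AUC. Under linear disposition AUC does not depend on infusion duration. A model-based AUC could avoid the problem, provided the model receives the actual infusion and sampling times, which the plan does not say.
- For the overlay, silence is not a decision to ignore duration. A model can take infusion time as an input, and programming rules and table shells sit in separate documents (SAP 9 and 11). On the prediction intervals, the plan is unspecified rather than wrong.
- It is tempting to assume that start and stop times are already required. The PK analysis set asks only for sufficient dosing information, without defining it.
- Half-lives and the share of long infusions are assumptions, and at low shares the pooled shift is small. PK is exploratory, with no test or acceptance criterion.

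What survives is that SAP 5.5.1 states a grouping rule, that the rule mixes unlike end-of-infusion samples, and that it omits the dose level named in protocol 9.5.1.5.1.

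**Conclusion.** The point holds as a minor one. Given linear disposition, the direction of the duration effect is certain. Its size is not: the ratio for an individual end-of-infusion concentration runs from about 0.48 to 0.95 over assumed initial half-lives of 5-60 minutes, and the shift in a pooled mean may be only a few percent if the 15-minute option is seldom used. The omission of dose level from SAP 5.5.1 needs no such assumption, since it is a plain mismatch with the protocol.

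The effect is confined to the exploratory, descriptive PK tables and the exposure-comparability display. The response analysis and the recommendation for each histology do not depend on it. Nothing here shows that the comparability conclusion will be wrong, only that the planned displays could not separate infusion practice from a PK difference.

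**What to change.** 1. In SAP 5.5.1, summarize post-infusion concentrations by dose level, which reconciles the SAP with protocol 9.5.1.5.1, and by actual infusion duration (5 minutes or less versus longer). Day 8 pre-infusion samples may stay pooled across duration.
2. State in the SAP that actual infusion start and stop times and actual sample times are recorded and used. This also covers the Cycle 1 draws that follow the ECG.
3. Carry the overlay into the SAP. Generate its prediction intervals from those actual times, and compare with observed reference concentrations only at like duration, where the reference duration is known.

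No infusion regimen, visit or sample changes. The cost is SAP wording, an additional table split, and confirmation that the case report form captures the times. The downside is small rows: at an assumed 20% share of 15-minute infusions, 0.20 × 15 = 3 children per histology against 0.20 × 45 = 9 overall. The duration split may therefore be shown for all cohorts combined rather than within histology.
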